### Escalation Visits (3-8 visits depending upon starting point and progress)

Visits 2 (week 8), 3 (week 16), 4 (week 24), 5 (week 32), 6 (week 40), 7(week 48), 8 (week 56), 9 (week 64) for increasing amounts of peanut (visit length 2-3 hours). These visits stop at week 64 or when 1 Tablespoon (equivalent) is reached.

Attempt to increase daily ingestion by open oral food challenge to next amount higher. Maximum amount is 3 teaspoons/equivalent.

- Physical exam, vital signs, medical history
- Blood samples, Visit 3, week 16 (before feeding challenge commences; not to exceed 5cc/kg on a single day or 9.5ml/kg over any eight-week period per NIH guidelines)
- Spirometry or peak flow (optional under age 7)
- Open oral food challenge to amount determined by DBPCFC (Section 3.1.3) unless at top amount
- Training/review on measuring amounts for home use
- Collection/Provision of diaries and contact instructions
- Saliva and stool collection (visit 3)
- Quality of life survey, diet questionnaire (visit 3)

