### Control Arm

Participants in the control arm will receive monthly telephone follow up and reporting of any allergic reactions, including reporting accidental exposure to peanut, and will keep a diary. The diary will be accessed for the following issues: ate peanut, and any reaction, symptoms or illnesses. These will be confirmed/reviewed monthly by telephone, email (printout as source) or in person visit to evaluate that the entries match what the experience is. This will be documented on an eCRF (or email print out) and the clinical team will add any diary entries if needed. They will have a visit 16 weeks following the initial DBPCFC for review of avoidance instructions and collection of a blood sample, saliva and stool for mechanistic studies, and QoL and diet questionnaires. The control arm subjects will undergo a DBPCFC and procedures listed under desensitization DBPCFC (above) are performed at a time determined by a surveillance algorithm (see Section 13.3). Control arm participants do not require follow up for SU. Those unable to tolerate the DBPCFC will pursue clinical management off of the study, those who tolerate the full feeding may add peanut to the diet "ad lib" but with at least one weekly serving recommended and pursue clinical care off of the study.

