### 8.4 Unscheduled Visits

If disease activity increases or other concerns arise between regularly scheduled visits, participants will be instructed to contact study personnel and may be asked to return to the study site for an "unscheduled" visit. If the participant becomes/is unable to ingest at least 1/8 teaspoon of peanut butter, they will undergo a supervised feeding of 1/16th teaspoon, which is the lowest amount permitted and may become the daily amount if tolerated. If the participant cannot ingest 1/16th teaspoon of peanut butter they will be considered a treatment failure and will stop any daily ingestion, but will undergo the endpoint DBPCFCs at 72 weeks.

The following circumstances may lead to unscheduled visits (active arm):

1. Concern regarding peanut ingestion triggering increased chronic symptoms (e.g., increased eczema, gastrointestinal symptoms).

Procedures (1-8 hour visit):

- Physical exam, vital signs, medical history
- Spirometry (or peak flow under age 7, or if spirometry not allowed per COVID protocols)
- DBPCFC to the amount being ingested on a daily basis, or supervised open feeding of the amount ingested on a daily basis, or supervised feeding of a lower amount, as deemed necessary for full evaluation

The PI/Investigator and family will determine whether to continue daily ingestion, reduce the daily amount, or follow off intervention, and/or refer for additional medical evaluation (i.e., endoscopy).

2. Concern regarding acute symptoms from home ingestion.

Participants will be instructed to contact the PI/Investigator/study team for acute allergic symptoms (with the exception of oral pruritus, mild transient abdominal discomfort, or perioral redness/hives). The investigator will determine the best course of action, with possible actions being the following:

- 1. Continue with daily home dosing
- 2. Return for an observed ingestion of the same amount
- 3. Return for an observed ingestion of a step lower amount.
- 4. Discontinuation of ingestion

The following process algorithm will be applied regarding symptoms associated with the daily ingestion.

If the subject only experiences oral/pharyngeal pruritus, or perioral redness/hives, or mild transient abdominal discomfort, the daily ingestion may continue. Instructions about eating peanut with meals will be reviewed. If the symptoms are bothersome or persistent, procedures per #1 above (chronic symptoms) will be followed.

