### Table 2. Table of Events (does not include unscheduled visits)

Procedures	Screening /Baseline DBPCFC week 0, 3 days	Visit #1. Initial feeding with sub-threshold amount, week 1	Visit 2-9, evaluate to increase threshold, week 8,16, 24, 32, 40, 48, 56, 64 (all visits may not be needed depending upon escalation progress)	DBPCFC for desensitizatio n (active) or follow up (controls) Week 32, 56, 64 or 72	SU DBPCFC (24 weeks after desensitization DBPCFC for those on active peanut
Informed consent, screening, complete	All				

Procedures	Screening /Baseline DBPCFC week 0, 3 days	Visit #1. Initial feeding with sub-threshold amount, week 1	Visit 2-9, evaluate to increase threshold, week 8,16, 24, 32, 40, 48, 56, 64 (all visits may not be needed depending upon escalation progress)	DBPCFC for desensitizatio n (active) or follow up (controls) Week 32, 56, 64 or 72	SU DBPCFC (24 weeks after desensitization DBPCFC for those on active peanut
medical history, demographic questions					
Physical assessment, vital signs, spirometry, interval medical assessment	All	Intervention group	Intervention group	All	Intervention group passing desensitization
Pregnancy test (urine) for females of child bearing potential	All			All	Intervention group passing desensitization
DBPCFC as per PRACTALL protocol, up to cumulative dose 9043	All			All	Intervention group passing desensitization
Open peanut feeding for threshold		Intervention group	Intervention group		
Skin prick testing	All			All	Intervention group passing desensitization
Blood sample , stool and saliva collection	All		All, week 16	All	Intervention group passing desensitization
Quality of life questionnaire, diet survey	All		All week 16	All	Intervention group passing desensitization
Review adverse events and home food administration diary, report all			All (including monthly call [monthly review call not	All	Intervention group passing desensitization

Procedures	Screening /Baseline DBPCFC week 0, 3 days	Visit #1. Initial feeding with sub-threshold amount, week 1	Visit 2-9, evaluate to increase threshold, week 8,16, 24, 32, 40, 48, 56, 64 (all visits may not be	DBPCFC for desensitizatio n (active) or follow up (controls) Week 32, 56, 64 or 72	SU DBPCFC (24 weeks after desensitization DBPCFC for those on active peanut
			depending upon		
			escalation		
			progress)		
food allergic			performed if		
reactions (both			an in-person		
randomized groups)			visit occurs;		
			monthly calls		
			continue until		
			last study		

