# 12.3 Grading and Attribution of Adverse Events

# 12.3.1 Grading Criteria

The study site will grade the severity of adverse events experienced by the study subjects according to the criteria set forth in the National Cancer Institute's Common Terminology Criteria for Adverse Events (NCI-CTCAE, 5.0), with the exception of anaphylaxis which will be graded according to the scale included in the definition section This document (referred to herein as the NCI-CTCAE manual) provides a common language to describe levels of severity, to analyze and interpret data, and to articulate the clinical significance of all adverse events. The NCI-CTCAE has been reviewed by the PI/Co-I and has been deemed appropriate for the subject population to be studied in this protocol.

Adverse events will be graded on a scale from 1 to 5 according to the following standards in the NCI-CTCAE manual:

Grade 1 = mild adverse event.

Grade 2 = moderate adverse event.

Grade 3 = severe and undesirable adverse event.

Grade 4 = life-threatening or disabling adverse event.

Grade 5 = death.

Only events grade 2 or higher and SAEs will be recorded on the appropriate AE case report form for this study.

For grading an abnormal value or result of a clinical or laboratory evaluation (including, but not limited to, a radiograph, an ultrasound, an electrocardiogram etc.), a treatment-emergent adverse event is defined as an increase in grade from baseline or from the last post-baseline value that doesn't meet grading criteria. Changes in grade from screening to baseline will also be recorded as adverse events, but are not treatment-emergent. If a specific event or result from a given clinical or laboratory evaluation is not included in the NCI-CTCAE manual, then an abnormal result would be considered an adverse event if changes in study therapy or monitoring are implemented as a result of the event. For additional information and a printable version of the NCI-CTCAE manual, consult the NCI-CTCAE web site: http://ctep.cancer.gov/reporting/ctc.html.

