### **12.4.2 Collecting Adverse Events**

Adverse events (including SAEs) may be discovered through any of these methods:

- Observing the subject.
- Interviewing the subject [e.g., using a checklist, structured questioning, diary, etc.] .
- Receiving an unsolicited complaint from the subject.
- In addition, an abnormal value or result from a clinical or laboratory evaluation can also indicate an adverse event, as defined in Section 12.3, *Grading and Attribution of Adverse Events*.

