6.5.2.4 Adverse Events

Individual adverse events will be summarized as the number (%) of events and number and (%) of patients with the event in peanut ingestion and avoidance subjects. Adverse events will be modelled using Poisson regression and the rate of individual adverse events will compared between randomization arms through the desensitization DBPCFC visit. Long-term adverse events will be evaluated for those in the intervention group who are tested for sustained unresponsiveness following the desensitization DBPCFC visit. The Safety population will be used for this analysis.

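### Adverse events are looked for more intensively in the peanut arm before the endpoint visit, so the rate comparison in SAP 6.5.2.4 may overstate that arm's relative rate

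*Protocol*

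**What the plan says.** **Scheduled assessment.** Table 2 has a row for "Physical assessment, vital signs, spirometry, interval medical assessment". It is marked for all participants at baseline and at the endpoint challenge, but for the intervention group alone at Visit 1 and Visits 2-9. Protocol 8.3 agrees: the escalation visits open with "Physical exam, vital signs, medical history" and add spirometry or peak flow, which is optional under age 7. For controls, 8.3 says "They will have a visit 16 weeks following the initial DBPCFC for review of avoidance instructions and collection of a blood sample", together with saliva, stool and questionnaires. It lists no examination, vital signs or spirometry at that visit.

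**Unscheduled assessment.** After a general opening that applies to any participant, Protocol 8.4 introduces its specific triggers with "The following circumstances may lead to unscheduled visits (active arm").

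**Routes to an adverse event.** Protocol 12.4.2 lists observation, interview or diary, and unsolicited complaint, and then says that "an abnormal value or result from a clinical or laboratory evaluation can also indicate an adverse event". Section 12.3.1 restricts recording to grade 2 or higher and SAEs. For results that the CTCAE manual does not cover, "an abnormal result would be considered an adverse event if changes in study therapy or monitoring are implemented as a result".

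**Analysis.** SAP 6.5.2.4 specifies Poisson regression, in which "the rate of individual adverse events will compared between randomization arms through the desensitization DBPCFC visit". Neither that section nor Protocol 13.4.4 makes any provision for unequal ascertainment.

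**The concern.** Safety compared with avoidance is a stated secondary objective (Protocol 2.3, SAP 2.2). A rate comparison between arms is interpretable only if an event of a given kind has about the same chance of being recorded in either arm. Here one route to the adverse-event form, a finding made by a clinician on examination or by spirometry, is open repeatedly in one arm and closed in the other until the endpoint visit.

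The direction of the resulting bias is known: it counts against peanut. A larger sample would not remove it. SAP 6.6 treats secondary p-values as descriptive, but that does not help, because the estimated rate ratio itself is shifted. An excess due to surveillance could be read as a harm of daily peanut.

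**Working it through.** **1. Reproduce the plan's own visit count.** The inputs are the ladder in SAP 3.1.1 (1/8, 1/4, 3/8, 1/2, 3/4, 1, 1.5, 2, 3 tsp, i.e. nine rungs), 8-week steps, and the starting amounts by baseline reaction dose in Protocol 3.1.3.

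- Escalations = rungs from the starting amount up to 3 tsp.
- Examinations before the endpoint = Visit 1 + escalations.
- Endpoint week = 8 × escalations + 8.

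| Baseline reaction dose | Start | Escalations | Intervention exams | Control exams | Endpoint week |
|---|---|---|---|---|---|
| 443 mg | 1/8 tsp | 8 | 9 | 0 | 72 |
| 1043 mg | 1/4 tsp | 7 | 8 | 0 | 64 |
| 2043 mg | 3/8 tsp | 6 | 7 | 0 | 56 |
| 5043 mg | 1 tsp | 3 | 4 | 0 | 32 |

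The escalation counts match the protocol's heading "Escalation Visits (3-8 visits depending upon starting point and progress"), and the weeks match Table 2 (32, 56, 64 or 72). The counts are for a child on schedule. A failed step adds visits, up to Visit 9; a missed or discontinued one removes them.

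**2. Separate what both arms share from what they do not.**

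| Route to an adverse event | Intervention | Control |
|---|---|---|
| Diary of reactions, symptoms, illnesses | yes | yes |
| Monthly contact and adverse-event review | yes (a visit replaces the call in visit months) | yes |
| Unsolicited complaint; general route to an unscheduled visit | yes | yes |
| Specific unscheduled-visit triggers (8.4) | yes | not listed |
| Scheduled exam, vital signs, spirometry before the endpoint | 4 to 9 times | 0 |
| Exam at the endpoint visit | yes | yes |

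What controls miss is mainly a finding that needs an examination or spirometry, is not noticed or reported by the family, reaches grade 2, and has gone by the endpoint visit.

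**3. Illustrate the size.** The documents give neither an event rate nor a detection rate, so everything in this step is an assumption. Let q be the share of recorded intervention-arm events known only from those examinations. With equal true rates and equal follow-up, controls record a fraction (1 − q) of the intervention count, so the null rate ratio is 1/(1 − q):

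- q = 5%: 1/0.95 = 1.05
- q = 10%: 1/0.90 = 1.11
- q = 20%: 1/0.80 = 1.25

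To translate q, assume 36 children per arm, equal strata and 1 recorded event per intervention child. Mean examinations are (9 + 8 + 7 + 4)/4 = 7, or 36 × 7 = 252 in the arm. Then q of 5%, 10% or 20% means 1.8, 3.6 or 7.2 exam-only findings, which is 0.7%, 1.4% or 2.9% of examinations.

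Simulated Poisson counts at that event rate, with a two-sided 5% test of the log rate ratio, give a false-positive chance of about 5% at q = 0, 7% at q = 10% and 14% at q = 20%. At q = 20% it ranges from 9% to 24% as the rate goes from 0.5 to 2 events per child. These are pooled all-event figures, whereas the SAP compares individual events, for which q could be nil or much larger.

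**The case against.** **Much of what matters is symptomatic.** The safety endpoint consists of acute allergic reactions, anaphylaxis and gastrointestinal side effects, which a diary and a monthly call capture in both arms. Table 2 marks adverse-event review for all participants. Controls have a full examination at the endpoint visit, inside the comparison window. The grade 2 threshold probably removes many incidental findings. All of this stands, and it makes the affected set narrow.

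**Stronger readings that a reader might infer, and why they fail.**

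- *That events in the peanut arm cannot be found in controls.* The shared routes above contradict this. Asthma, eczema or intercurrent illness that causes symptoms can be reported from either arm.
- *That the 12.3.1 rule can be met only with peanut.* The rule names monitoring as an alternative to study therapy, and monitoring can change for a control. It also covers only results outside the CTCAE manual.
- *That 12.3.1 counts every successive rise in grade, so counts grow with the number of visits.* The post-baseline reference there is a value that does not itself meet grading criteria, and the sentence defines treatment emergence. It does not set a rule for counting repeated rises.
- *That unscheduled visits are closed to controls.* The opening of 8.4 tells participants generally to make contact if concerns arise and says they may be asked to return. Only the specific triggers are listed for the active arm, and most of them concern ingestion.

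**Dropping events from the main comparison could bias it the other way.** In visit months the visit replaces the call, so a parent-reported event may first be told at an escalation visit. Excluding everything found at visits would undercount harm from peanut. This objection is sound and shapes the fix.

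**Conclusion.** The concern holds in a limited form. Scheduled assessment before the endpoint is 4 to 9 examinations against none, and the SAP has no safeguard. The Poisson comparison may therefore overstate the peanut arm's relative event rate, through findings of grade 2 or higher that need an examination or spirometry.

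The visit counts follow from the documents for children on schedule. The size of the bias does not: 1.05, 1.11 and 1.25 rest on assumed exam-only shares of 5%, 10% and 20%, and the true share could be smaller. Reactions to supervised or home peanut feeding are genuine effects of the intervention and are no part of this bias. The primary endpoint and its sample size are unaffected. This is a cheap improvement to a secondary comparison; it does not invalidate the safety plan.

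**What to change.** Keep the all-event comparison in SAP 6.5.2.4 and add a pre-specified companion:

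1. **Exclude** from the companion rate comparison only adverse events known solely from examination, vital signs or spirometry at visits that controls do not have.
2. **Retain** every event reported by participant or parent, whether first told by call, diary or visit; all SAEs; and all reactions to supervised or home peanut feeding.
3. **List** the excluded findings separately for the intervention arm.
4. **Identify** them by a field on the adverse-event eCRF recording how the event was found, or from source records for past events. Visit and event dates alone do not show this.
5. **State the interpretation in advance:** an excess seen only in the all-event analysis is possibly due to surveillance.

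The SAP's opening statement allows revision before data lock. The cost is one eCRF field, some retrospective coding and a few sentences of SAP text, with no added visits or procedures and no change to safety reporting. The downside is possible misclassification of how an event was found, especially for past events. The companion also leaves in place the difference between in-person and telephone contact. The wording of 12.3.1 can stay.

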# **12.3.2** Attribution Definitions

The relationship, or attribution, of an adverse event to the study therapy regimen or study procedure(s) will initially be determined by the site investigator or Sponsor-investigator and recorded on the appropriate AE eCRF. Final determination of attribution for safety reporting will be determined by the Sponsor-Investigator. The relationship of an adverse event to study therapy regimen or procedures will be determined using the descriptors and definitions provided in Table 12.3.2.

Code	Descriptor	Relationship (to primary investigational product and/or other concurrent mandated study therapy or study procedure)			
UNRELATED CATEGORY					
1	Unrelated	The adverse event is clearly not related: there is insufficient evidence to suggest a causal relationship.			
RELATED CATEGO	RELATED CATEGORIES				
2	Possible	The adverse event has a reasonable possibility to be related; there is evidence to suggest a causal relationship.			
3	Definite	The adverse event is clearly related.			

### Table 12.3.2 Attribution of Adverse Events

### 12.4 Collection and Recording of Adverse Events

### 12.4.1 Collection Period

Adverse events will be collected from the time of the onset of the event until a subject completes study participation or until 30 days after he/she prematurely discontinues (without withdrawing consent) or is withdrawn from the study by the investigator.

### **12.4.2 Collecting Adverse Events**

Adverse events (including SAEs) may be discovered through any of these methods:

- Observing the subject.
- Interviewing the subject [e.g., using a checklist, structured questioning, diary, etc.] .
- Receiving an unsolicited complaint from the subject.
- In addition, an abnormal value or result from a clinical or laboratory evaluation can also indicate an adverse event, as defined in Section 12.3, *Grading and Attribution of Adverse Events*.

### **12.4.3** Recording Adverse Events

Throughout the study, the investigator will record adverse events and serious adverse events as described previously (Section 12.2, Definitions) on the AE/SAE eCRF regardless of the relationship to study therapy regimen or study procedure.

The investigator will treat subjects experiencing AEs appropriately and observes them at suitable intervals until their symptoms resolve or stabilize. Once recorded, an AE/SAE will be followed until it resolves with or without sequelae, or until the end of study participation, or until 30 days after the subject prematurely withdraws (without withdrawing consent)/or is withdrawn from the study, whichever occurs first.

### **12.5** Reporting of Serious Adverse Events and Adverse Events

### **12.5.1** Reporting of Serious Adverse Events

This section describes the responsibilities of the Sponsor- investigator to report serious adverse events. Timely reporting of adverse events is required by 21 CFR and ICH E6 guidelines.

Site investigators will report all serious adverse events to the Sponsor-Investigator (see Section 12.2.3, *Serious Adverse Event*), regardless of relationship or expectedness within 24 hours of discovering the event. The Sponsor investigator will inform the DAIT NIAID Medical Monitor and Sponsor Medical Monitor in real time

For serious adverse events, all requested information on the AE/SAE CRF will be provided. However, unavailable details of the event will not delay submission of the known information. As additional details become available, the AE/SAE CRF will be updated and reported.

### **12.5.2** Reporting to Health Authority

The Sponsor-Investigator of the IND has the responsibility of reporting all AEs and SAEs to the FDA within the reporting time limits set forth by the FDA. It is the Sponsor-investigator's responsibility to report any serious adverse event to the Sponsor Medical Monitor at his site and to the NIAID Medical Monitor within 24 hours of becoming aware of the event.

After an adverse event requiring 24-hour reporting (per Section 12.5.1, *Reporting of Serious Adverse Events to Sponsor*) is reported by the site investigator and assessed by Sponsor-Investigator, there are two options for reporting the adverse event to the FDA:

